# 5.3. Ongoing consent

At each hospital/clinic visit, the participant's willingness to continue in the trial will be ascertained and documented in the medical notes. Where participant-reported data is sent directly to the Trials Office, or via the F4S App, the completion of this data will be taken as tacit consent that the participant wishes to continue in the trial.

Throughout the trial, the participant will have the opportunity to ask questions about the trial. Any new information that may be relevant to the participant's continued participation will be provided. Where new information becomes available which may affect the participants' decision to continue, participants will be given time to consider and if happy to continue will be re-consented. Re-consent will be documented in the medical notes. The participant's right to withdraw from the trial will remain.

# 6. ENROLMENT, RANDOMISATION AND BLINDING

# 6.1. Identification, screening and enrolment

Patients with suspected or confirmed lung cancer who are being considered for surgery will be identified and screened for eligibility from preoperative clinics and Multi-Disciplinary Team meetings (MDTs), and through referral letters for surgery. Patients will be identified by the direct care team such as lung cancer nurses, dietitians, physiotherapists, physicians and surgeons and research teams in these centres as well as at lung cancer MDTs. Surgical trainee research networks will also be used to help identify patients as members attend

these MDTs. On occasion, this identification may take place at Patient Identification Centres (PICs). These PICs feed into the main sites where the surgery will take place.

Once potential participants have been initially identified and screened according to the eligibility criteria, a member of the clinical (surgery or cancer) team will approach the patient at their next consultation appointment, provide a PIS and ask if they are willing to speak to a member of the site research team to find out about the trial in more detail, and assess their willingness to take part in the trial.

Patients may also be contacted prior to surgery by the direct care team to discuss their willingness to take part in the study and in this situation each patient will be sent an ethically approved PIS and appropriate site contact details should they want any further information.

Regardless of the route of approach, the patient will be asked if they wish to participate in the trial (following the process below) and, if not, whether they would be willing to share their reasons for declining, for purposes of the SWAT.

An appropriately trained member of the team (healthcare professionals) delegated the task on the **F4S-2 Site and Signature Delegation Log** will confirm eligibility. If the potential participant meets all eligibility criteria and confirms they are willing to take part in the trial, they will be asked to formally consent to participate in the trial.

Details of all patients approached about the trial will be recorded on the **F4S-2 Participant Screening/Enrolment Log,** which will be kept in the ISF, and should be available to be sent to the Trials Office upon request.

#### 6.2. Randomisation

### 6.2.1 Randomisation System

Randomisation will be provided by BCTU using a secure online system (available at <insert web address>), thereby ensuring allocation concealment. Unique log-in usernames and passwords will be provided to those who wish to use the online system and who have been delegated the role of randomising participants into the study as detailed on the F4S-2 Site Signature and Delegation Log. These unique log-in details must not be shared with other staff and in no circumstances should staff at sites access the system using another person's login details. The online randomisation system will be available 24 hours a day, 7 days a week, apart from short periods of scheduled maintenance.

In the event of the online system being unavailable the research team will contact the BCTU Trial Office (between 9am and 5pm) who will randomise the participant using a process on paper which will later be added to the database.

#### 6.2.2 Randomisation Procedure

After participant eligibility has been confirmed and informed consent has been received, the participant can be randomised into the trial using the online system. All questions and data items on the online randomisation form must be answered prior to a potential participant being randomised into the trial and a trial number being issued.

Following randomisation, a confirmatory e-mail will be sent to the local PI and the person who carried out the randomisation.

The PI or delegate should add the participant to the **F4S-2 Participant Recruitment and Identification Log**, which links participants with their trial number. The PI or delegate must maintain this document securely at the NHS site, which is not for submission to BCTU, and should be held in strict confidence.

#### 6.2.3 Randomisation Method

Participants will be randomised at the level of the individual in a 1:1 ratio to either the F4S App with usual care or usual care alone. A minimisation algorithm will be used within the online randomisation system to ensure balance in the treatment allocation over the following variables:

- Smoking History: current (within the last 14 days) or non/past smoker
- Age: 18-39, 40-69, 70-79, ≥80
- BMI: <18.5, ≥18.5-24.9, ≥25-29.9, ≥30

To avoid the possibility of the intervention allocation becoming predictable, a 'random element' will be included in the minimisation algorithm. Full details of the randomisation specification will be stored in a confidential document at BCTU.

# 6.3. Blinding

Given the nature of the intervention, it is not possible to blind the clinical teams or the participant to the randomisation allocation, so the participant reported outcomes will be completed with knowledge of treatment allocation.

# 6.4. Informing the participant's GP

The participant's General Practitioner (GP) will be notified that they are in F4S-2 trial, using the **F4S-2 GP Letter.** 

### 7. TRIAL INTERVENTION

Participants will be randomised to receive:

Usual care

OR

• F4S App and Usual care

#### 7.1. Usual Care

This may be a range of healthcare services that provides all or one of the following: information for the participants (with or without links to further information), formal rehabilitation via physiotherapy, dietician support via dietician, and/or routine follow up as per standard of care.

# 7.2. F4S App and Usual Care

This will combine the usual care interventions as per section 7.1 and use of the F4S App (for a minimum of 2 weeks prior to surgery) with details described in the following sections.

## 7.3. F4S App

The advice given to the participant is determined by their unique, dynamic, personal health status. That is, as a participant engages with the App, the advice regarding exercise and nutrition adapts.

Specifically, the App collects baseline demographic data, comorbidities, symptom burden using simple questions and Visual Analogue Scales (VAS), and the outcome measures of Quality of Life, Health and wellbeing scores. This information is used to deliver personalised feedback, support and guidance when using the App. e.g. if diabetic, guidance on avoiding a hypoglycaemic event. This will not constitute trial data and is part of the data to inform the intervention itself.

The digital programme or 'App' comprises three prehabilitation interventions:

#### 7.3.1 Structured Home Exercise Programme

Participants are guided through a series of screens to build their own programme, including a range of strengthening, mobility and cardiovascular exercises. Baseline suggestions on programme level/ intensity are made based on a 'sit to stand test' conducted within the App. Once the programme is built, participants are encouraged to exercise daily to achieve

.....

150 minutes of exercise/week as per pulmonary rehabilitation guidelines [38]. Heart rate is recorded using a wearable sensor provided free of charge to the participants. Once each exercise is completed, the participant inputs their perceived intensity using the BORG perceived exertion scales to the App [40]. This data is used to encourage the participant via personalised messages to increase or decrease intensity at the next session to achieve the target intensity of BORG perceived exertion as per rehabilitation guidelines [38]. Regular data uploads allow health care professionals to view participants' progress, whilst the App allows the participant to request support from the health care professional if required. Only these health care professionals can view the information within the App. They will be able to see alerts from the participant through the admin page. The App app has safety messages to advise participants to seek medical advice when required (in the same way that usual care patients are directed to contact depending on the situation)

Participants are also able to record any other exercise they undertake e.g. swimming, running etc. Whilst the programme is focussed on pre-surgery, exercise can also benefit recovery post-surgery [41], so the participant will be permitted to use the programme after surgery for a period of 6 weeks, but it will be adapted/reset according to participants' post-surgery 'sit to stand test' performance (on postoperative day 1).

### 7.3.2 Individualised Nutritional Conditioning

At the time of enrolment, participants complete a nutritional screening questionnaire (Patient-Generated Subjective Global Assessment (PG-SGA score)) within the App [42], which tailors' nutritional advice and supplementation based on symptoms and nutritional risk. All participants in the F4S arm will be encouraged with the aid of a "ready reckoner" to intake a high protein (20g) snack within 90 minutes of exercise to stimulate muscle protein synthesis and a positive protein balance. Participants will record in the App when they have taken a protein snack. Participants deemed 'Medium risk' (PG-SGA score 4-9) will be started on a low volume, high calorie, high protein oral nutritional supplement (ONS) containing at least 18g of protein twice a day until surgery. High risk participants (score > 9) will be started on supplements as above and referred to a dietitian for optimisation of supplement prescription [42, 43].

While the recommendations above are aligned with national guidance, sites can adhere to local policies. Standard care will be followed regarding the supplementation and monitoring.

Whilst the programme is focussed on pre-surgery, it is acknowledged that after surgery, calorie and protein requirements are high at a time when intake may be impaired by the after effects of surgery. Therefore, nutritional intervention will continue for 4 weeks post-

surgery. Participants will complete the PG-SGA using the App on postoperative day 1 and based on this nutritional advice and supplementation will be tailored as described above.

#### 7.3.3 Personalised Health Information

[figure not shown]
Displayed within the App as short informational videos with subtitles. Information is responsive, and guided by symptom data and whether the participant is pre- vs. post-surgery, as recorded in the App. For example, if the participant reports feeling breathless, information on how best to manage this is displayed. Information on surgery is prominent to the participant before surgery, whilst recovery and symptom management e.g., pain control are prominent after. Further details of the programme can be found on www.Fit4surgery.uk.

[figure not shown]
Motivational processes – In App data collection will include Motivational processes underpinning engagement with the App/behaviour change, autonomous and controlled motivation for engagement in exercise and physical activity and an assessment of autonomy, competence, and connection.

#### 7.3.4 Technical training and competency for the intervention

Participants will receive initial training by the research team at recruitment on how to use the App (i.e., set up the programme, complete questionnaires, how to seek help), and will be provided with web links for short training and troubleshooting videos, as well as a pictorial paper guide. There is also a technical helpline that the participant can contact if they have difficulty with the App. Research staff will undertake web-based training to deliver the initial guidance, in which their competency will also be assessed and recorded.

Figure A and B: Screen shots of the Fit for Surgery App showing types of exercise, modifications, real-time feedback screen and exercise summary

#### 7.4. Intervention Modification or Cessation

The F4S App will not be available to participants who are randomised to the usual care arm of the trial, so crossover will not be possible from usual care. It is possible that participants randomised to the F4S arm will cease to engage with the App completely. This will not however be considered a crossover, since this is part of the pragmatic nature of the trial.

As mentioned in section 7.3 the App is designed to adapt to the participant as they use it, or cease to use it. The variability in engagement with the App forms part of the trial and will be captured by the App.

### 7.5. Continuation of intervention after the trial

The App is designed specifically to assist participants in the weeks immediately prior to, and subsequent from, their surgery. Therefore, there is no further benefit expected after the 6 week trial period is completed.

The App will remain available for use where participants have used their own devices to download and access it, and may continue to use it. This will not be within the confines of the trial. It will be explained to participants that whilst use may continue, no further benefit is expected after the 6 week trial period is complete and it will not be monitored by the clinical team.

For participants who are provided with a tablet, the tablet will be returned and wiped of all data.

# 7.6. Intervention Access Supply and Storage

Participants will be asked to download the F4S App to their personal device. A link to register for the App will be provided to all participants randomised to the F4S arm. For those who do not have a mobile device, tablets will be provided before surgery and for approx. 6 weeks after. The tablet devices will be distributed to the recruiting sites from the Trial Office, where they should be safely secured until provided to a participant.

When provided to a participant the equipment log should be completed to record tablet use. At the end of each participant's participation in the trial the tablet will be returned to the recruiting site. The site will maintain a log of usage of the Tablet, set used throughout the study recording the lot number used against each participant (on an equipment log). The hardware does not require any special storage conditions but should be handled with due care and in accordance with any instructions. Equipment failures will be replaced provided there is no evidence of inappropriate use or deliberate negligence, under which circumstances the Sponsor reserves the right not to re-supply the participant.

# 7.7. Device and Tablet support

Site staff will be trained on how to use the F4S App and training documents will be provided within the ISF. This will include informing participants how to set up, register and use the App.

The devices will be provided with no other software installed and only the F4S App preinstalled. Participants will be asked not to use the tablet for any other purpose than for trial participation.

Hardware support will be provided by the third-party App developer, with reference documentation provided to site staff to ensure the devices are wiped at the end of trial participation.

#### 7.8. Adherence

Adherence to the intervention arm will be defined as using the app at least twice a week in the time before surgery and the completion of quality of life questionnaires 30 days after surgery.

Adherence to usual care will be the completion quality of life questionnaires 30 days after surgery.

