## 8. OUTCOME MEASURES

#### 8.1. Internal Pilot Outcome

The success of the 6-month internal pilot study will be based upon the recruitment rate (overall and at individual sites), completeness of primary outcome data (quality of life questionnaires 30 days after surgery in each arm of the study) and adherence to the intervention (adherence in the intervention arm will be defined as using the App at least twice a week in the time before surgery).

We will recruit 125 participants (14% of the total sample) during the 6-month internal pilot phase. We will open 2 sites in the first month, then 3 sites a month for the next 5 months until a maximum of 17 sites are open in the pilot phase.

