### 15.2.4 Missing data and sensitivity analyses

Every attempt will be made to collect full follow-up data on all study participants; it is thus anticipated that missing data will be minimal. Participants with missing primary outcome data will not be included in the primary analysis in the first instance. This presents a risk of bias, and sensitivity analyses will be undertaken to assess the possible impact of the risk. In brief, this will include a multiple imputation approach where missing data not at random will be imputed using multivariate imputations by chained equations following the methods of White and colleagues [56]. Twenty imputation cycles will be used, as this has previously been demonstrated to produce adequate results [57,58].

A compiler average causal effect analysis (CACE) (only those patients who are compliant with treatment allocation) will be carried out to assess the effect in those who adhered to their randomised allocation [55].

The different elements of the intervention (Nutrition, Exercise and Health information) and use/access to rehabilitation services (eg. Maggies centres) will be analysed to assess the effect is consistent across the treatment group. This will be performed with the inclusion of an interaction term.

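### The pilot's adherence criterion counts App use and returned questionnaires, and neither shows that exercise or nutrition was delivered

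*Protocol*

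**What the plan says.** Section 7.8 begins: "Adherence to the intervention arm will be defined as using the app at least twice a week in the time before surgery". The sentence goes on to make this a joint condition: "using the app at least twice a week in the time before surgery and the completion of quality of life questionnaires 30 days after surgery". For the comparator it says: "Adherence to usual care will be the completion quality of life questionnaires 30 days after surgery". Section 8.1, on the internal pilot, gives only the first half: "adherence in the intervention arm will be defined as using the App at least twice a week in the time before surgery".

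Section 2.1 sets a pilot aim of at least 80% adherence to the F4S intervention. The last row of Table 1 (section 8.1) turns this into bands: Stop below 50%, Modify 50 to 79%, Go 80 to 100%. The footnote to that row points to section 7.8.

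Section 7.3 describes three components: exercise, nutrition and health information. On exercise, section 7.3.1 says "Once the programme is built, participants are encouraged to exercise daily to achieve" a weekly total of "150 minutes of exercise/week as per pulmonary rehabilitation guidelines". The participant enters a Borg rating after each exercise, a wearable sensor records heart rate, and other exercise can be entered. On nutrition, section 7.3.2 says "Participants will record in the App when they have taken a protein snack". Section 7.3.3 describes the information component as short videos.

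Section 15.2.4 plans a complier average causal effect (CACE) analysis, which "will be carried out to assess the effect in those who adhered to their randomised allocation". It does not define adherence again. Table 3 (section 12.1) says that usage and engagement data go from the App to the trials unit as electronic files.

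**The concern.** A criterion labelled adherence to the intervention should tell the oversight committees whether the intervention was received. Here a participant who opens the App twice a week to watch a video, and later returns the day-30 booklet, is adherent. One who exercises as encouraged but does not return the booklet is not. The second condition describes data collection, which Table 1 already covers in a separate row.

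At stake is the Stop/Modify/Go decision on adherence. The pilot could report Go on this row while exercise and nutrition were little used, and the committees would lose the chance to respond at the stage meant for it. A secondary stake is the CACE, for which section 7.8 is the only adherence definition in the protocol. There, complier status would depend partly on return of the day-30 questionnaires that supply one of the two primary outcomes.

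**Working it through.** **What each condition requires**

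- App use at least twice a week (sections 7.8 and 8.1): a use is not defined by sessions, minutes, snacks or supplements. Because videos are one of the three components, the minimum exercise is 0 of 150 minutes a week and the minimum number of snack records is 0.
- Day-30 questionnaires (section 7.8 only): exercise 0, nutrition 0.
- Both together: still 0 and 0.

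**How many participants produce a Go**

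- Inputs: pilot n = 125 and 1:1 allocation (sections 6.2.3 and 8.1); Go from 80% (Table 1).
- The pilot share reproduces: 125 / 902 = 13.9%, stated as 14%.
- App arm: 125 / 2 = 62.5, so 62 or 63 participants.
- Go from 0.80 × 62 = 49.6, rounded up to 50, or 0.80 × 63 = 50.4, rounded up to 51. None of these need have logged any exercise.

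**Whether the two definitions can give different decisions**

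Suppose, for illustration, that the App arm sits exactly at 80% on App use and at 80% on questionnaire return.

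- Section 8.1 wording: 80%, which is Go.
- Section 7.8 wording (both conditions): at most 80%, if the same people fail both, and at least 0.80 + 0.80 − 1 = 60%. If the two are independent, 0.80 × 0.80 = 64%.
- Except at the upper limit, section 7.8 gives Modify where section 8.1 gives Go. The passages must therefore be reconciled whatever is done about exercise.

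**Whether the main design depends on the definition**

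- Inputs for the Comprehensive Complication Index (section 15.1): difference 5, SD 19.0, two-sided 2.5%, power 90%, attrition 20%.
- n per arm = 2 × 19² × (2.241 + 1.282)² / 5² = 358.4, so 359. Then 359 / 0.80 = 448.75, so 449 per arm and 898 in total, against 902 stated.
- The figure reproduces to within 3%, and adherence does not enter it. The modified intention-to-treat analysis in section 15.2 ignores adherence by design.

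**The case against.** The best defence is that App use is the randomised treatment. Section 7.2 defines the arm as usual care plus use of the App, watching a video is receipt of one component, and section 7.4 treats variable engagement as part of a pragmatic trial. A low, broad threshold also suits a CACE. The method assumes that allocation has no effect on those classed as non-compliers, and this is easier to believe for people who hardly opened the App than for people who used its advice but logged little exercise. Adherence is only one of six rows in Table 1, and even a Go leads to a review of trial processes. Section 15.2.4 plans to examine nutrition, exercise and information separately, so the exercise and nutrition data are not ignored.

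Much of this stands. App use is a legitimate measure and should be kept, including as the main compliance variable in the CACE. It does not justify presenting App use alone to the committees as adherence to a programme of exercise, nutrition and information. Nor does it explain the questionnaire condition or the difference between sections 7.8 and 8.1.

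Two stronger readings are tempting:

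- *Twice a week is too little against a daily schedule.* Daily exercise is encouraged, not required. Twice is a floor. Two sessions of 150 / 2 = 75 minutes would reach the weekly total, and section 1.2.1 cites benefit from 1 to 3 sessions a week.
- *The CACE will understate the effect in those who exercised.* That requires App users who did not exercise to gain nothing from the other components, which the protocol does not state. The link from the CACE to section 7.8 is also an inference from wording, and a statistical analysis plan may define compliance otherwise.

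**Conclusion.** The point holds for the pilot adherence criterion. As written, the Go band can be met by about 50 participants with no evidence that any exercise or nutrition was delivered, and sections 7.8 and 8.1 can place the same data in different bands. The Table 1 link is explicit and needs no assumption. The 60 to 80% range rests on the assumed 80% rates. The protocol does not say how many participants would use the App without exercising, so the size of any gap between engagement and delivery is unknown.

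A reader might infer that the trial's main result is at risk. It is not: the primary analysis and the sample size do not use adherence. A reader might also infer that the exercise logs will be discarded. The documents do not show that. The general wording of Table 3 may include them, but it does not name them. Section 7.3 places the App's personalisation data outside the trial data, and section 20 removes server data at the end of the trial, so the matter should be settled expressly.

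**What to change.** - In sections 7.8 and 8.1 and in the Table 1 footnote, use one definition. Call App use at least twice a week before surgery engagement, and say what counts as a use.
- Remove questionnaire completion from adherence in both arms and leave it to its own Table 1 row.
- Beside engagement, report the percentage of App-arm participants with App-logged exercise sessions in each week before surgery, and the percentage with protein-snack records. Ask the oversight committees to judge adherence on both. This needs no new exercise or nutrition target.
- In Table 3, name the exercise entries (Borg rating, heart rate, other exercise) and the snack records as part of the data transfer from the App.
- In section 15.2.4, keep App use as the main compliance variable. Add logged exercise as a further sensitivity analysis, and state that it assumes no effect through the other App components in participants below the exercise criterion.

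The cost is protocol and analysis-plan wording and a check of the transfer specification. No visit, participant or new measurement is added. The reported delivery figure will probably be lower than the engagement figure. The logs are partly self-reported, so unlogged exercise will be missed.
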